6.9. Concomitant Therapy

The summary and reporting of concomitant therapy has been described in the CPMP SAP version 5. As described in Section 6.2, painDETECT will additionally be included as a covariate for modelling rescue medication.

Concomitant therapy will be reported for the first 4 weeks of the double-blind period (active-treatment phase) and separately for the entire 8 weeks of the double-blind period.

6.10. Efficacy Analyses

6.10.1. Primary Outcome and Methodology

Analysis of the primary outcome has been described in CPMP SAP version 5. The longitudinal model will include average pain intensity as measured by the NRS during the preliminary data-entry period (PDEP, last 7 days prior to randomization at Visit 3) and within each nominal week of the double-blind treatment period as a longitudinal outcome. As noted in Section 4.1, endpoint for the primary analysis is defined as 4 weeks post initial treatment administration.

Calculation of the weekly or biweekly time intervals used for analysis of weekly or biweekly mean scores from the eCOA device will follow the algorithm described in CPMP SAP Section 6.12.1, except that the end of the final interval will be determined based on the last visual analog scale (VAS) result collection date or the last scheduled visit start date if VAS results are missing for the last scheduled visit.

6.10.2. Additional Analyses of the Primary Outcome

Borrowing placebo information by pooling from Studies H0P-MC-BP01 and H0P-MC-BP03 for the evaluation of treatment effect on the mean change from baseline in average pain intensity as measured by the NRS (and secondary outcomes of worst pain intensity as measured by the NRS and VAS) will be performed following the description in CPMP SAP version 5, Section 6.12.1. Descriptive statistics of primary outcome variables by demographics, disposition, disease characteristics, and treatment administration may be summarized by ISA to examine the population homogeneity assumption between ISAs.

6.10.3. Secondary Efficacy Analyses

Secondary efficacy analyses common to all ISAs within CPMP have been described in the CPMP SAP version 5. Unless otherwise specified, the time point for secondary endpoint measurements is the same as that for the primary endpoint. Study BP02 will also consider the following secondary analyses.

The RMDQ is a simple, sensitive, and reliable method to measure disability in patients with back pain. The RMDQ consists of 24 statements relating to the person's perceptions of back pain and associated disability based on:

- physical ability/activity
- sleep/rest
- psychosocial
- household management
- eating, and
- pain frequency.

Participants are asked if they feel the statement is descriptive of their own circumstance on that day. The total score is obtained by counting the number of “Yes” responses, ranging from 0 = no disability to 24 = maximal disability.

A Bayesian longitudinal mixed-effect model repeated measures (MMRM) analysis will be performed to evaluate the change from baseline to each postbaseline visit in the RMDQ total score. The model will utilize the constrained cell means model so that a common mean is estimated at baseline. More details on this approach are provided in the CPMP SAP version 5.

This table describes information included in the model.

Categorical effects	the interaction of treatment and time point (constrained to estimate a common mean at baseline across treatments) average baseline pain severity category (baseline NRS < 7, baseline NRS ≥ 7) presence of neuropathic pain (painDETECT ≥ 19, painDETECT < 19) pooled investigative site
Continuous covariates	none

Abbreviation: NRS = numeric rating scale.

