6.2. Adjustments for Covariates

The general adjustment strategy has been described in the CPMP SAP version 5.

Randomization into Study BP02 is stratified by the presence of neuropathic pain as defined by the painDETECT score. The following stratification factor will be included in the models for the primary, secondary, and some exploratory outcomes.

Neuropathic pain	painDETECT score
Positive presence	≥ 19
Unclear or negative	< 19

The painDETECT total score is derived from patient responses to 9 questions on the painDETECT questionnaire. Seven questions ask about the gradation of pain, scored from 0 to 5 (never = 0, hardly noticed = 1, slightly = 2; moderately = 3, strongly = 4, very strongly = 5). One question asks about the pain course pattern, scored from -1 to 2, depending on which pain course pattern diagram is selected. Another question asks about radiating pain, answered as yes or no and scored as 2 or 0, respectively. The final score is between -1 and 38, and a score of 19 or higher suggests that pain is likely to have a neuropathic component (Freyhagen et al. 2006).

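### In the RMDQ model of SAP 6.10.3 only treatment interacts with time point, so the painDETECT and baseline-severity terms adjust the Week 4 contrast only in part and its interval may be slightly wider than needed

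*SAP*

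**What the plan says.** The RMDQ analysis in SAP 6.10.3 is a Bayesian MMRM intended "to evaluate the change from baseline to each postbaseline visit in the RMDQ total score". Baseline is part of the response vector: "The model will utilize the constrained cell means model so that a common mean is estimated at baseline".

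The table of model terms then lists:
- Treatment, which is the only factor allowed to vary over time: "the interaction of treatment and time point (constrained to estimate a common mean at baseline across treatments".
- Baseline severity, as a two-level category split at an NRS score of 7, and site after pooling; each is a single term.
- The stratification factor, also as a single term: "presence of neuropathic pain (painDETECT ≥ 19, painDETECT < 19".

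No continuous covariates are listed, and no covariate other than treatment has a time interaction. For further detail the section refers to CPMP SAP version 5, which is not among the documents.

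SAP 6.2 states that randomisation is stratified by painDETECT category and adds: "The following stratification factor will be included in the models for the primary, secondary, and some exploratory outcomes". For the primary outcome, SAP 6.10.1 says: "The longitudinal model will include average pain intensity as measured by the NRS during the preliminary data-entry period". Baseline pain is therefore an outcome there too, but the model terms are left to the CPMP SAP. SAP 4.1 sets the endpoint at Week 4 (Visit 5), and SAP 4.2 places RMDQ change among the other secondary endpoints.

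**The concern.** In an MMRM on change scores, a single painDETECT term allows mean change to differ between the two painDETECT categories. The same term does something else once baseline is an outcome. Its one coefficient applies to baseline and to every later visit, so the model assumes the same mean change within an arm in both categories. The adjustment for the stratification factor is then weaker than a reader of SAP 6.2 would expect.

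What is at stake is interval width. If painDETECT or severity predicts change in RMDQ, the part of that prediction which the single term cannot absorb stays in the residual covariance and widens the interval for the Week 4 contrast.

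**Working it through.** **Plan's own figure.** The documents give no SD, correlation, effect size or precision for RMDQ, so there is nothing to reproduce. The stated inputs are about 150 randomised and 85% completing (150 × 0.85 = 127.5). The allocation ratio is redacted.

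**Algebra.** Let a binary covariate X have true effects γ0 at baseline and γj at visit j. The listed terms give E[Y0] = μ0 + βX and E[Yj] = μ(treatment, j) + βX.
- Fitted change: E[Yj − Y0] = μ(treatment, j) − μ0. β cancels.
- Conditional on baseline, with b = cov(Yj, Y0)/var(Y0), the coefficient of X is β(1 − b). The correct one is γj − bγ0. With one β for baseline and all visits, the two match throughout only if γ is constant over time.
- With equal baseline means, the Week 4 contrast is a post-baseline difference conditional on baseline. β(1 − b) is not zero in general, so the contrast does get a restricted adjustment.

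**Size: assumptions, none in the documents.** SD 5; correlations 0.6 (baseline–Week 2), 0.5 (baseline–Week 4) and 0.7 (Week 2–Week 4); painDETECT ≥ 19 in 25%; complete data at baseline, Week 2 and Week 4; the likelihood counterpart of the Bayesian model (the priors are not in the documents).

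**Formula.** The contrast variance is proportional to V = S44 − S04²/S00. Here S is the residual covariance: the true covariance plus p(1 − p)(γ − β)(γ − β)′, with β chosen to minimise det S. The allocation factor cancels in ratios.

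Worked case, effects 0, 1.5, 3 at baseline, Week 2 and Week 4, with p(1 − p) = 0.1875 and fitted β = 1.432:
- S00 = 25 + 0.1875 × 1.432² = 25.384
- S44 = 25 + 0.1875 × 1.568² = 25.461
- S04 = 12.5 − 0.1875 × 1.432 × 1.568 = 12.079
- V as written = 25.461 − 12.079²/25.384 = 19.713
- V with covariate-by-time = 25 − 12.5²/25 = 18.75
- V with no covariate = 25 + 0.1875 × 3² − 12.5²/25 = 20.438
- Excess as written = 19.713/18.75 − 1 = 5.1%; with no covariate, 9.0%

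The last column below is a REML simulation with n = 150 at 2:1, stratified, painDETECT term only.

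| painDETECT effect (baseline, Wk 2, Wk 4) | β | V none | V as written | V by time | Excess as written, formula | Excess, simulation |
|---|---|---|---|---|---|---|
| 2, 2, 2 | 2.000 | 18.93 | 18.75 | 18.75 | 0.0% | 0.0% |
| 2, 3, 4 | 2.955 | 20.39 | 19.18 | 18.75 | 2.3% | 2.4% |
| 0, 1.5, 3 | 1.432 | 20.44 | 19.71 | 18.75 | 5.1% | 5.3% |
| 2, 1, 0 | 1.045 | 18.93 | 19.18 | 18.75 | 2.3% | 2.4% |

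In SE terms, √1.024 = 1.012 and √1.053 = 1.026. In the fading case (2, 1, 0) the single term does worse than leaving the covariate out.

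**Range.** A two-visit version of the formula, with correlation 0.4 to 0.8 and prevalence 0.3 or 0.5, gives these SE excesses per covariate: 0.2% to 1.1% if the effect on change is 0.2 SD, 1.5% to 6.7% at 0.5 SD, and 3.7% to 16% at 0.8 SD.

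**Width or precision.** A second simulation used effects 0, 2, 4, N = 128 at 1:1, correlation 0.6, prevalence 0.3 and 400 runs. SEs are listed as no covariate / as written / by time:
- Stratified: model 0.774 / 0.749 / 0.705; empirical 0.721 / 0.727 / 0.724.
- Unstratified: model 0.772 / 0.747 / 0.705; empirical 0.751 / 0.723 / 0.683.

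Under stratification the estimate itself is equally variable in all three models, and only the reported SE changes. Without stratification the estimate is more variable as well.

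**The case against.** The strongest reply has four parts.

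First, a reader might infer that the single terms cannot adjust at all. The algebra and the figures say otherwise: in the 0, 1.5, 3 case the single term brings the excess down from 9.0% to 5.1%. This objection stands against any claim of no adjustment. It does not remove the remaining shortfall.

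Second, nothing in the documents shows that painDETECT or severity effects on RMDQ change between baseline and Week 4. That also stands. Every non-zero figure above depends on an assumed path, and with a constant effect there is no excess.

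Third, one might translate the excess into lost participants. For painDETECT that is not supported, because stratified allocation has already removed its contribution to the variability of the estimate. The loss is real only for an unstratified covariate. SAP 6.2 names painDETECT alone as a stratification factor; whether baseline severity is also one is left to the CPMP documents.

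Fourth, CPMP SAP version 5 may specify the time interactions, and SAP 6.2 promises only that the factor will be in the models, which it is. So no commitment is breached. Even so, the 6.10.3 table is presented as the content of the RMDQ model and lists no such terms, so the gap is in the BP02 text itself.

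**Conclusion.** The point holds for the RMDQ model as a modest, conditional inefficiency. As listed, the painDETECT and severity terms drop out of the fitted change and adjust the Week 4 contrast only in part. If their effects shift by 2 to 3 RMDQ points (0.4 to 0.6 of the assumed SD) between baseline and Week 4, the model-based variance is about 2% to 5% too large under the assumed inputs. A larger shift or a higher correlation would raise it. The treatment estimate is unbiased, and any error makes the interval wider, not narrower.

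Two wider readings are tempting but not supported. One is that the primary NRS model has the same fault: its terms are in CPMP SAP version 5, so this cannot be judged from the documents. The other is that it carries over to the RMDQ responder models in SAP 6.10.3.1, which reuse the covariate list. Responder status exists only after baseline, so a single covariate term does not cancel there.

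**What to change.** In the SAP 6.10.3 table, replace the baseline NRS category and painDETECT category terms with their interactions with time point, baseline included. Keep pooled site as a main effect: the same argument applies to it in principle, but it may have many levels, and each would need a coefficient at every visit.

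For the primary NRS model, check CPMP SAP version 5. Make the same change only if these interactions are not already there, and cross-refer from SAP 6.2 so that the form of the adjustment is clear.

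The cost is SAP wording and one line of model code. In a baseline/V4/V5 fit each covariate has three coefficients instead of one, so two extra parameters. When the covariate effect is constant over time, the variance cost is under 1%.

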6.10.3.1. Other Secondary Analysis

The proportion of participants in each treatment group meeting prespecified binary efficacy outcomes will be calculated for each postbaseline time point and will be used to compare treatment groups. The prespecified binary efficacy outcomes include the proportion of participants:

- with a reduction greater than or equal to 30%, 50%, and 70% from baseline as measured by the RMDQ score, and
- with at least a 3.5-point reduction from baseline in the RMDQ score.

A Bayesian pseudo-likelihood-based categorical repeated measures model will be used to estimate the proportion of participants in each treatment group meeting the prespecified threshold for each postbaseline time interval up to Week 4 (or visit up to Visit 5) and separately up to Week 8 (or visit up to Visit 7). These estimates will be used to compare treatment groups. More details on this approach are provided in the CPMP SAP version 5.

The model will include the categorical and continuous covariates described for the secondary analysis of RMDQ total score.

In addition, time to first treatment response from baseline based on the prespecified binary thresholds above will be assessed. Analyses will be conducted according to the time to event analyses specified in the CPMP SAP version 5.

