4.2. Secondary Objectives

Secondary objectives applicable to all ISAs are listed in the CPMP SAP version 5.

Additional secondary endpoints specific to Study BP02 are listed below.

Objective	Endpoint Measure
Other Secondary	
Physical Functioning Efficacy of LY3526318 versus placebo	
 Mean change from baseline to endpoint in RMDQ total score Proportion of participants with reduction from baseline of at least 3.5 points in RMDQ total score at each time point Proportion of participants with reduction from baseline greater than or equal to 30%, 50%, and 70% in RMDQ total score at each time point Time to first treatment response with at least 30%, 50%, and 70% reduction from baseline in RMDQ total score

Abbreviation: RMDQ = Roland-Morris Disability Questionnaire.

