6.7. Participant Characteristics

The summary of participant characteristics has been described in the CPMP SAP version 5.

ISA-specific considerations are described below:

painDETECT ≥ 19 (that is, positive for neuropathic pain)

Roland-Morris Disability Questionnaire (RMDQ) total score at baseline.

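### As written in the BP02 SAP, the RMDQ responder models list no baseline RMDQ term; adding one is a cheap precision gain whose size and location depend on inputs the documents do not give

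*SAP*

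**What the plan says.** SAP 4.2 lists the RMDQ responder endpoints under 'Other Secondary'. One is: "Proportion of participants with reduction from baseline of at least 3.5 points in RMDQ total score at each time point". The others are reductions of at least 30%, 50% and 70%.

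SAP 6.10.3 analyses the RMDQ mean change with a Bayesian repeated-measures model and says: "The model will utilize the constrained cell means model so that a common mean is estimated at baseline". Its table lists the treatment-by-time interaction, baseline NRS category (below 7, or 7 and above), painDETECT category (below 19, or 19 and above) and pooled site. The entry for continuous covariates is 'none'.

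SAP 6.10.3.1 analyses the responder endpoints at postbaseline time points with a Bayesian pseudo-likelihood categorical repeated-measures model, and says of its covariates: "The model will include the categorical and continuous covariates described for the secondary analysis of RMDQ total score".

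Two passages defer to a document that was not supplied. SAP 6.10.3.1 says of this model: "More details on this approach are provided in the CPMP SAP version 5". SAP 6.2 says: "The general adjustment strategy has been described in the CPMP SAP version 5".

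**The concern.** The covariate list was written for a model in which baseline RMDQ is already present as an outcome with a common mean. There, having no continuous covariate is reasonable. Carried over to a binary response with no baseline value, the same list leaves baseline RMDQ out altogether. Baseline NRS category measures pain, not disability, and is dichotomised, so it stands in for baseline RMDQ only indirectly.

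Whether a participant responds on a change score depends on where that participant started. At stake is some precision in the responder comparisons. The primary NRS analysis and the RMDQ mean-change analysis are not affected.

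**Working it through.** **1. The plan's own figures.** None is given for the RMDQ responder endpoints. SAP 5.2 gives about 150 randomised and 85% completing: 150 × 0.85 = 127.5. The allocation ratio is redacted, so 85 vs 42 (2:1) and 64 vs 64 (1:1) completers are both assumed.

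**2. Why the gain moves between thresholds.** Let b be the slope of follow-up on baseline: b = ρ × SD(follow-up) / SD(baseline). Response means that the follow-up score is at or below a cut-off that itself rises with baseline. The cut-off's slope is 1 for a fixed 3.5-point drop and 0.7, 0.5 and 0.3 for 30%, 50% and 70% reductions. Ignoring floor and ceiling, response depends on baseline through the gap, cut-off slope minus b. A gap near zero leaves baseline nothing to explain.

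**3. Simulation.** All inputs are assumptions.
- Baseline mean 12, SD 5; placebo change 2; effect 2. Scores are rounded and limited to 0-24.
- Latent correlation with baseline RMDQ is 0.3 for NRS category and 0.2 for painDETECT category. There are five sites.
- The model is a single-visit logistic model with a weak normal prior (SD 5 on the log-odds), standing in for the planned repeated-measures model. There are 6000 trials per setting.
- The result is the variance of the standardised responder difference with baseline RMDQ, divided by the variance without it. Below 1 is a gain. Both versions contain NRS category, painDETECT category and site. Monte Carlo error is about 0.01.

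Each cell shows the gap, then the variance ratio, at 85 vs 42:

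| Follow-up SD, ρ | b | 3.5 points | 30% | 50% | 70% |
|---|---|---|---|---|---|
| 5, 0.5 | 0.50 | 0.50; 0.863 | 0.20; 0.985 | 0.00; 1.010 | -0.20; 1.001 |
| 5, 0.7 | 0.70 | 0.30; 0.906 | 0.00; 1.009 | -0.20; 0.990 | -0.40; 0.977 |
| 6, 0.5 | 0.60 | 0.40; 0.919 | 0.10; 0.999 | -0.10; 1.001 | -0.30; 0.986 |
| 6, 0.7 | 0.84 | 0.16; 0.965 | -0.14; 0.999 | -0.34; 0.963 | -0.54; 0.934 |
| 6.5, 0.5 | 0.65 | 0.35; 0.950 | 0.05; 1.003 | -0.15; 0.998 | -0.35; 0.976 |
| 6.5, 0.7 | 0.91 | 0.09; 0.986 | -0.21; 0.987 | -0.41; 0.947 | -0.61; 0.912 |

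At 64 vs 64 the ranges are 0.842-0.987 (3.5 points), 0.971-1.004 (30%), 0.948-1.009 (50%) and 0.919-1.000 (70%).

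**4. Sensitivity.** Fourteen further settings varied ρ from 0.4 to 0.8, baseline mean from 10 to 14, NRS-RMDQ correlation from 0 to 0.5, and effect 0 or 2. The ranges are 0.819-1.005 (3.5 points), 0.943-1.007 (30%), 0.872-1.012 (50%) and 0.843-1.018 (70%). At SD 6.5, ρ 0.8 (b = 1.04; gaps -0.04 and -0.74), the 3.5-point ratio is 1.005 and the 70% ratio 0.843, so the order of the first table row reverses.

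**5. A second simulation with other assumptions.** It covers 24 settings: baseline mean 9, 12 or 14; ρ 0.4, 0.6 or 0.75; placebo drop 3; effect 1.5; additive or proportional change; no sites. It reports the gain in effective sample size, (1 - R² without) / (1 - R² with) - 1. A gain g corresponds to a variance ratio of 1/(1 + g).
- 3.5 points: 1.4-25.6%. The maximum is 1/1.256 = 0.80.
- 30%: 0-5.3%. The maximum is 1/1.053 = 0.95.
- 50%: 0-10.8%. The maximum is 1/1.108 = 0.90.
- 70%: 0-17.7%. The maximum is 1/1.177 = 0.85.

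The 3.5-point threshold gained most in 17 of the 24 settings. In the other 7 it was the 70% threshold; these had ρ 0.75, or ρ 0.6 with follow-up SD 6.

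In power terms (effect 2.5, 64 per arm, follow-up SD 5.5), the 3.5-point comparison goes from 64.2% to 69.2% at ρ 0.6 and from 81.6% to 83.3% at ρ 0.75. The 30% comparison stays at 71.1% at ρ 0.6.

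**6. Chance imbalance is the same effect, not a second one.** At SD 5, ρ 0.5, baseline imbalance explains 12.6% of the unadjusted variance of the 3.5-point difference, and adjustment removes 1 - 0.863 = 13.7%. At SD 6.5, ρ 0.7, both figures for the 70% threshold are 8.8%.

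**The case against.** The strongest objection is that there may be no gap. The BP02 SAP is an appendix-level plan that defers both the general adjustment strategy and the details of this model to CPMP SAP version 5, and it says what the model will include, not that nothing else may enter. That stands: the documents supplied show that the term is not listed here, not that it is absent from the analysis. A reader might infer a demonstrated omission; the documents do not support that. Even so, a programmer working from the BP02 text alone would leave baseline RMDQ out.

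The second objection is that the benefit is small. That also stands in part. The median of the six 3.5-point ratios in the table is (0.919 + 0.950)/2 = 0.935, and √0.935 = 0.967, an interval about 3% narrower. The mean ratios are 0.997 at 30%, 0.985 at 50% and 0.964 at 70%, and many 30% and 50% entries are within Monte Carlo error of 1. The endpoints are 'Other Secondary', and SAP 6.4 plans no multiplicity adjustment.

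The third objection is that the figures come from a single-visit stand-in with an assumed prior, five assumed sites and an assumed allocation. That is true, so they show direction and order of size, not a forecast. Sparse 70% responses deserve care: at 85 vs 42 the simulated placebo arm has 2.4 to 5.8 expected responders out of 42, and two or fewer in 6-57% of trials. The Wald test there has a type I error of 0.016-0.045 against a nominal 0.05, so no power claim is made for that threshold.

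**Conclusion.** The point holds as a precision improvement. The BP02 text gives the responder models no baseline RMDQ term, and the device that supplies it in the mean-change model has no counterpart for a response defined only after baseline.

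Under the assumed inputs the variance of a responder difference falls by roughly 0-20%, and the worst simulated loss is about 2%. The range describes the settings tried and is not a bound. Which threshold gains depends on the baseline-to-follow-up correlation and the follow-up SD, and the documents give neither.

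Two stronger readings are tempting. One is that the omission biases the responder comparison or is an error. It is neither: randomisation makes the comparison valid without the term, and mean simulated differences agreed to within 0.001 with and without it. The other is that the benefit lies mainly at the 3.5-point threshold. That is so at low to moderate correlation, but it reverses at high correlation.

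**What to change.** First check CPMP SAP version 5.

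- If it already includes baseline RMDQ in this model, cite that section in SAP 6.10.3.1 and reconcile it with the entry 'none' for continuous covariates in SAP 6.10.3.
- If it does not, add to SAP 6.10.3.1: *The responder models will also include baseline RMDQ total score as a continuous covariate.*

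Because the odds ratio then becomes conditional on baseline, report treatment-group proportions averaged over the observed baseline distribution, unless CPMP SAP version 5 already defines how proportions are estimated.

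The cost is one or two sentences, one parameter and a small programming step. No new data are needed: SAP 6.7 already summarises "Roland-Morris Disability Questionnaire (RMDQ) total score at baseline". The downsides are an extra parameter where 70% responses are sparse, and a linear term that does not capture participants who cannot respond at 3.5 points. On an integer score a 3.5-point reduction means at least 4 points, so anyone starting at 3 or below is a certain non-responder: about Φ((3.5 - 12)/5) = Φ(-1.7) = 4.5% at the assumed mean 12 and SD 5.
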